The use of a validated symptom score with long term follow-up could yield important information for the choice of treatment of hemorrhoidal disease.

Postoperative complications and adverse effects

Serious complications to hemorrhoidal operations occur rarely. The most commonly early complications are urinary retention, bleeding or fever/infection. Late complications are anal fissure, anal stenosis and anal incontinence. A Cochrane review reported after open hemorrhoidectomy; postoperative bleeding 2.9%, urinary retention 5.1%, anal fissure 3.1%, anal stenosis 0,9% and anal incontinence 1.6%²⁰.

Search Methods

A PubMed database search was conducted with following PICO query:

```
((("haemorrhoids"[All Fields] OR "hemorrhoids"[MeSH Terms] OR "hemorrhoids"[All Fields]) AND (((Open[All Fields] AND ("hemorrhoidectomy"[MeSH Terms] OR "hemorrhoidectomy"[All Fields] OR "haemorrhoidectomy"[All Fields])) OR Milligan-Morgan[All Fields]) OR ("diathermy"[MeSH Terms] OR "diathermy"[All Fields]))) AND (Ligasure[All Fields] OR (Ligasure[All Fields] AND ("hemorrhoidectomy"[MeSH Terms] OR "hemorrhoidectomy"[All Fields] OR "haemorrhoidectomy"[All Fields]))) AND ("complications"[Subheading] OR "complications"[All Fields])
```

A Cochrane was done searching for h(a)emorroidectomy and h(a)emorroid.

Relevant articles were chosen and by title and abstract and by reading the reference lists further texts were identified. In addition Danish and Swedish guidelines from national medical journals were included.

OBJECTIVES

Aim

To analyze and compare the long-term effects of LigaSure™ hemorrhoidectomy (LH) and Open Hemorrhoidectomy (OH) on hemorrhoidal symptoms.

Main outcome variable

Symptoms related to hemorrhoids one year postoperatively, according to a validated hemorrhoidal symptom score (HDSS)(appendix 3).

Secondary outcome variable

- 1) Patient satisfaction with the operation one year postoperatively, evaluated on a seven grade Lichert scale.
- 2) Quality of Life as evaluated by Short health Scale (SHS), Short Form 36 (SF36) and EuroQualityofLife -5 Dimensions (EQ-5D-5L) (appendix 6).
- 3) Anal continence as evaluated by the Wexner score⁴⁵, the Revised Fecal Incontinence Scale (RFIS) ⁴⁶.

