We will also analyze: anal function with anal manometry, anatomical result as evaluated by the surgeon, operation time, theatre time (time consumed in the operating room), postoperative complications, postoperative pain and need of analgesics, length of postoperative hospital stay and days before return to work or possibility of return to work.

SUBJECT CRITERIA

Subject Inclusion Criteria

In order to be eligible to participate in this study, an individual must meet all of the following criteria:

- Male or female aged 18 to 85 at the time of randomization
- Grade III-IV hemorrhoids and grade II hemorrhoids refractory to previous treatment with rubber band ligation or sclerotherapy.
- Hemorrhoidal symptom score of four or more
- Colonoscopy, sigmoidoscopy or rigid rectoscopy within 3 months before inclusion.
- American Society of Anesthesiologists (ASA) score of I or II. (day-care surgery)
- Provide signed and informed consent form

Subject Exclusion Criteria

An individual who meets any of the following criteria will be excluded from participation in this study:

- Previous operation of grade III and IV hemorrhoids within the last 2 years.
- Previous operation for anal incontinence.
- Active anal fistula or anal fissure
- Incontinence for solid stool

- Active immunosuppressive therapy (increased risk of anorectal sepsis)
- Cirrhosis / portal hypertension
- Mb Crohn⁴⁷

DESIGN AND METHOD

Trial Design

This is a single center randomized clinical trial comparing two operative techniques in the treatment of hemorrhoids.

Qualification of the surgeons

The surgeon should have experience from at least ten open hemorrhoidectomies and ten LigaSure™ hemorrhoidectomies before operating independently

Operation date and type of anesthesia

Operation time, theater time, operative bleeding, grading of complexity of the operation and type of anesthesia is recorded by the surgeon after the operation in “Protokol for operation” (appendix 8)

Study Interventions – Open Hemorrhoidectomy (OH)

Patient Material and Recruitment

According to the power calculation at least 62 subjects are needed for the analysis.

Compensating for an estimated loss to follow-up of approximately 10%, 70 subjects will be included in the study. See statistical considerations in a later chapter.

Subjects for this study will be recruited consecutively from patients attending the proctologic outpatient clinic at the department of surgery at Holbæk Hospital eligible for operation.

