Inclusion procedure

Subjects recruited will receive written information about the study (appendix 1).

Subjects will be offered a new appointment with one of the surgeons participating in the study offering further information if needed. It will be possible to bring an assessor.

Subjects will be offered 14 days to consider their participation. Before inclusion in the study a declaration of acceptance will be signed by the subject (Appendix 2). A checklist, “Protokol for inklusion” (appendix 5), will be used at the first visit in the surgical outpatient clinic to ensure correct inclusion and patient history will be obtained in “Protokol for anamnese” (appendix 4).

Randomization

Subjects fulfilling the inclusion criteria and accepting to participate in this study will be randomized to LH or OH. Randomization is stratified by gender. List for randomization will be obtained from www.random.org. Notes assigning the subject to either operation according to the randomization lists will be placed in sealed envelopes. Each envelope is assigned gender and number in the study (Male 1,2,3.. or Female 1,2,3..).

The envelope will be opened in the operating theatre after the patient has been anesthetized. Randomization lists and the sealed envelopes will be stored in a locked safe.

Anesthesia and thromboembolic prophylaxis

After consulting with surgeon and patient the anesthesiologist will decide type of anesthesia to use (general, spinal or epidural). Respecting any contraindications, patients will receive a preoperative perianal block with a total of 40ml of Ropivacaine 4,75mg/ml according to the technique described by Nyström et al⁴⁸.

All patients will receive thromboembolic prophylaxis with low molecular heparin unless contraindicated.

STUDY INTERVENTION The operation methods

Operations will be done in the outpatient day surgery setting in the surgical department of Holbæk Hospital. Irrational details will be recorded in "Protocol for operation" (Appendix 8). In the following description of the two operative techniques differences in operation is marked in *italics*.

STUDY INTERVENTION Open Hemorrhoidectomy

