The procedure is repeated for each hemorrhoid taking care of leaving adequate "skin bridges" between each excision.

Postoperative Care

All patients will be discharged on the day of the operation unless there are any immediate postoperative complications or if the patient is living alone without attendance at home the first 24 postoperative hours.

Standard postoperative pain treatment is initiated for all patients regardless of operation type and consists of:

Paracetamol tablet 1-gram x4/day for 7 days, hereafter p.n.

Ibuprofen tablet 400mg x3/day for the first 7 days, hereafter p.n. (patients \geq 65 years old will receive supplementary Pantoprazole tablet 40mgx1/day when using ibuprofen)

Morphine tablet 10mg p.n. Max 6 tablets/day for 3 days

Magnesia tablet 1gx2/day for 7 days, hereafter p.n.

Xylocaine gel p.n.

At discharge from the hospital and in the preoperative material (appendix 1) patients are informed that there are no limitations concerning physical activity and they are encouraged to return to daily activity as soon they feel fit enough and the postoperative pain permits it. Patients are told not to drive, operate heavy machinery or performing other potentially dangerous tasks while on morphine.

Postoperative pain and return to daily activities

During the first 14 postoperative days the patient will report postoperative pain, use of analgesics and return to daily activities or work in "Patientdagbog" (appendix 10). Since weekends and holidays can influence when a patient returns to work, patients will answer a question when they feel fit enough to return to work. *It will also be noted if the patient is self-employed.*

Immediate postoperative course

Immediate postoperative complications, postoperative pain, use of analgesics and length of hospital stay will be noted in "Sygehusprotokol" (appendix 9).

Evaluation of symptoms

The questionnaire "Protokol for symptomer" (appendix 3) is used for evaluating hemorrhoidal symptoms recorded by the subject. Five questions on pain, itching, bleeding, soiling and prolapse graded from 0-4. Resulting in a score of 0-20.

The hemorrhoidal symptoms will be evaluated preoperatively at randomization, after 3 months, one-, three- and five years.

Patient's satisfaction with the operation will be evaluated on a 7-grade Lichert scale.

Evaluation quality of life

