Quality of life will be evaluated by SHS, SF-36 and EQ-5D-5L, recorded by the patient preoperatively at the randomization and one, three and five years postoperatively (appendix 7).

Evaluation of anal continence

Anal continence will be evaluated using both the Wexner score and the RFIS, registered by the patient in "protokol for symptomer" (appendix 3). Five questions with a score from 0-4 resulting in a total score of 0-20 for both operations. Evaluation will be done preoperatively at randomization, after 3 months, one-, three- and five years.

Anal function will also be analyzed with anal manometry preoperatively at randomization, after 3 months, one-, three- and five years. In addition we will investigate the amount of smooth muscle in the resected specimen from the two groups indicating the amount of injury to the internal anal sphincter.

Evaluation of hemorrhoidal anatomy

Hemorrhoidal anatomy is evaluated by the surgeon using “Protokol for anatomi”(appendix 7). Late postoperative complications are also reported in “Protokol for anatomi” at follow-up.

Hemorrhoids are graded according to the Goligher classification⁶:

Grade	Grade of prolapse
I	No prolapse, just prominent blood vessels
II	Prolapse upon bearing down or by physical exercise with spontaneous reduction
III	Prolapse upon bearing down and requires manual reduction
IV	Prolapse which cannot be manually reduced

Table 1: Goligher’s classification of internal hemorrhoids

The classification of hemorrhoids is based on physical examination by the surgeon and patient history. If prolapse is not present at physical examination the patient can be classified as having grade II or III based on the patient history. External skin flaps will also be recorded in “Protokol for anatomi” (Appendix 7).

Hemorrhoidal anatomy will be evaluated preoperatively at randomization, operatively and after 3 months, one-, three- and five years.

Security control

In order to detect adverse events and non-satisfactory results a security control of the study will be performed after operation of 10 patients in each arm. An open control of the immediate postoperative course, postoperative complications and postoperative hemorrhoidal symptoms three months after the operation will be performed.

STATISTICAL CONSIDERATIONS

Study Hypothesis

There is no difference in hemorrhoidal symptoms one year after an operation for hemorrhoids performed as LigaSure™ Hemorrhoidectomy or Open Hemorrhoidectomy.

Sample Size Considerations

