
The primary outcome variable is symptom score based on the patient questionnaire. The five questions graded from 0 to 4 results in a score from 0 to 20. Preliminary data from an ongoing study in our center comparing OH with THD and using the same questionnaire shows a symptom score after 3 months of 5 with a standard deviation (SD) of 4,2. The power calculator on www.stat.ubc.ca comparing the means for two independent samples with a two sided test has been used. We postulate that a difference of 3 points in symptom score would be clinically relevant with the standard deviation of 4,2. To demonstrate a difference in mean score of 3 points with a SD of 3.5 in both groups, an alpha error of 5% and a beta error of 20%, 31 patients in each group is needed.

As for the secondary objectives analyzing anal incontinence by the Wexner score and the Revised Fecal Incontinence Scale, both consists of five questions graded from 0 to 4 results in a score from 0 to 20. Preliminary data from the study mentioned above shows a mean of 4 and SD of 3,9 for the Wexner score and a mean of 2,3 with an SD of 3,9 for the RFIS. To demonstrate a difference in mean score of 3 points with a SD of 3.9 in both groups, an alpha error of 5% and a beta error of 20%, 27 patients in each group is needed.

Patient satisfaction is analyzed after year on a scale from 1 to 7. Preliminary data from the above-mentioned study shows a mean of 5,8 and a SD of 1,6. Assuming that a difference in 1,5 points would be clinically relevant 19 patients are needed in each group with an alpha error of 5% and a beta error of 20%.

Thus a sample size of 31 patients in each group should provide sufficient power in addressing analysis of primary and secondary endpoints. We estimate that there will be a loss of 9 patients for follow up. We will include 70 patients in the study.

ETHICS

The investigators will ensure that this study is conducted in full conformity with the principles set forth in the Declaration of Helsinki seventh edition⁵¹.

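### No analysis is specified for the one-year HDSS; prespecify ANCOVA on preoperative HDSS and gender, with the unadjusted comparison as sensitivity analysis

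*Combined protocol and SAP*

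**What the plan says.** The Précis and the section Main outcome variable fix the primary outcome as HDSS, scored 0 to 20, one year after the operation. Study Hypothesis gives only a null statement: "There is no difference in hemorrhoidal symptoms one year after an operation for hemorrhoids", for the two operations. Sample Size Considerations adds: "The power calculator on www.stat.ubc.ca comparing the means for two independent samples with a two sided test has been used". That sentence says how the trial was sized. No section states a test, model, covariate, effect estimate or confidence interval for the primary comparison.

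Two candidate covariates are already in the design:

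- Evaluation of symptoms: "The hemorrhoidal symptoms will be evaluated preoperatively at randomization, after 3 months, one-, three- and five years".
- Randomization: "Randomization is stratified by gender".

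Preoperative HDSS is otherwise used only for eligibility ("Hemorrhoidal symptom score of four or more", Subject Inclusion Criteria), and gender only for allocation.

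Sample Size Considerations prints two SDs for the primary outcome. The preliminary data are introduced with 4.2 ("shows a symptom score after 3 months of 5 with a standard deviation (SD) of 4,2"), but the sizing sentence reads "To demonstrate a difference in mean score of 3 points with a SD of 3.5 in both groups".

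**The concern.** Two things are at stake.

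**Precision.** If the calculator's method is carried over as the analysis, a preoperative measurement of the same score on the same patients goes unused. The envelope is opened only after the patient is anesthetized, so the preoperative score precedes knowledge of the allocation and is a proper covariate. At SD 4.2 the trial sits at the edge of 80% power, so free precision is worth having.

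**An open choice.** The text does not say whether the adjusted or the unadjusted result is primary. If that is decided after the data are seen, two tests of one hypothesis are available and the nominal 5% no longer holds exactly. The section Security control also provides for an open look at three-month symptoms after 10 operations per arm, which is a further reason to settle the model in writing.

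**Working it through.** **Inputs from Sample Size Considerations:** difference 3 points; SD 4.2 (3.5 also printed); two-sided 5%; 31 per arm; 70 enrolled with 9 lost, leaving 61.

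**Assumptions:** the correlation r between preoperative and one-year HDSS is not in the documents, so 0 to 0.5 is shown. SD 4.2 is a three-month value from another trial, applied here to one year as the plan does. Gender is taken as non-prognostic except in step 5.

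**1. The plan's figure.** With the normal approximation, n per arm = 2 × [(1.960 + 0.842) × SD / 3]². SD 4.2 gives 30.8, so 31, as stated. SD 3.5 gives 21.4, so 22. The stated 31 therefore rests on SD 4.2. At 31 per arm, power is 80.3% by the normal approximation and 79.0% by the t-test.

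**2. Unadjusted comparison, 31 per arm.** SE = 4.2 × √(2/31) = 1.067 on 60 df. Noncentral t power is 79.0%. The 95% CI half-width is 2.000 × 1.067 = 2.13 points.

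**3. ANCOVA with two covariates, 31 per arm.** SE = 4.2 × √(1 − r²) × √[(2/31) × (59/57)] on 58 df. The factor 59/57 is the average cost of chance imbalance in two covariates with 62 patients.

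| r | SE | Power | CI half-width |
|---|---|---|---|
| unadjusted | 1.067 | 79.0% | 2.13 |
| 0 | 1.085 | 77.6% | 2.17 |
| 0.2 | 1.063 | 79.2% | 2.13 |
| 0.3 | 1.035 | 81.3% | 2.07 |
| 0.4 | 0.995 | 84.3% | 1.99 |
| 0.5 | 0.940 | 88.1% | 1.88 |

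ANCOVA matches the unadjusted test at r = 0.19 and reaches 80% power at r = 0.24.

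**4. Other settings.**

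- 61 evaluable (31/30), SD 4.2: unadjusted 78.3%; ANCOVA 76.9%, 78.5%, 80.6%, 83.6% and 87.5% at r = 0, 0.2, 0.3, 0.4 and 0.5. It reaches 80% at r = 0.27.
- SD 3.5, 31 per arm: unadjusted 91.3%; ANCOVA 90.3% at r = 0 to 96.5% at r = 0.5.

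**5. Gender.** Simulation with 62 patients, 8,000 runs per setting, r = 0.3 and allocation balanced within gender (an assumption, since the plan does not mention blocking):

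| Variance explained by gender | Type I, unadjusted | Type I, ANCOVA | Power, unadjusted | Power, ANCOVA |
|---|---|---|---|---|
| 5% | 4.2% | 4.6% | 78.9% | 83.7% |
| 10% | 3.8% | 5.1% | 80.0% | 86.0% |

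If allocation is not balanced within gender, the unadjusted test rejects at 4.8% when gender explains 10%. Ignoring gender does not inflate the error rate; with balanced allocation it makes the test slightly conservative if gender is prognostic.

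**6. Open choice.** Always reporting the smaller p of the unadjusted and ANCOVA tests gives type I error of 5.6%, 6.1%, 6.5% and 7.3% at r = 0, 0.2, 0.3 and 0.5 (100,000 null trials each). Each test alone held 4.8% to 5.0%.

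**7. Bounded, skewed score.** One-year HDSS was simulated as beta-binomial on 0 to 20 with mean 5 and SD 4.2 (skewness 0.86). Baseline had an assumed mean of 9 and SD of 4.2 and was truncated at four or more; the documents give no baseline distribution. There were 20,000 trials per setting. ANCOVA type I error was 4.8% to 5.1%. For means of 8 against 5:

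| r | Unadjusted power | ANCOVA power |
|---|---|---|
| 0 | 78.7% | 77.1% |
| 0.25 | 78.8% | 79.9% |
| 0.38 | 78.1% | 83.1% |

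**The case against.** The strongest reply separates two claims. That no primary analysis is stated is a documented gap. That it should be ANCOVA is a recommendation: one sentence naming the two-sample comparison would also close the gap, would be valid, and would match the sizing. This stands as far as it goes, and the type I figures in particular argue for naming any one analysis.

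The benefit also depends on a correlation that the documents do not give. Below 0.19 ANCOVA loses a little power, at 0.2 it gains 0.2 points, and the entry floor of four may restrict the range of baseline scores and lower r. At SD 3.5 the power argument largely falls away. All of this stands, and it limits the size of the gain. It does not reverse the recommendation: at SD 4.2 the loss is at most about 1.5 points, against a gain of about 9 at r = 0.5.

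The case for gender is weaker than for baseline. If gender is unrelated to outcome, including it only costs a degree of freedom. It earns its place because allocation was stratified on it, and because it recovers power if it is prognostic.

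Finally, the type I figures are a worst case, and nothing in the plan suggests that anyone intends to choose by p-value.

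**Conclusion.** The concern holds. The plan fixes the endpoint but not its analysis, and it assigns no analytic role to the preoperative score or the stratification factor. This does not invalidate the trial, because an unadjusted comparison would be sound. It should still be changed: ANCOVA uses data already collected and is usually more precise.

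At the plan's SD of 4.2 and 31 per arm, power moves from 79.0% to between 77.6% and 88.1% as r runs from 0 to 0.5. The unknown r is the main uncertainty, followed by which SD applies at one year. Confidence in the gap is high; confidence in the size of the gain is moderate.

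**What to change.** Before one-year data are analyzed by arm, add a paragraph to Statistical Considerations that states:

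- **Primary analysis:** a linear model (ANCOVA) of one-year HDSS on operation, preoperative HDSS and gender.
- **Reported result:** the adjusted LH minus OH mean difference with its 95% CI and a two-sided 5% test.
- **Sensitivity analysis:** the unadjusted two-sample comparison of means, labelled as such.
- **Optional extension:** the same model for the Wexner and RFIS totals, each with its own preoperative value.

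The cost is one paragraph, with no new data, visits or patients. Statistically it is two degrees of freedom and at most about 1.5 points of power if both covariates are unrelated to outcome. The paragraph fixes only the adjustment and the test. Missing data and the analysis population must be specified separately, and the SDs of 4.2 and 3.5 in Sample Size Considerations need to be reconciled.

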Précis:	A randomized clinical trial that will compare two operations used for grade II - IV hemorrhoids. Patients referred to the department of surgery in Holbæk Hospital for hemorrhoids and eligible for operation will be included consecutively. Evaluation will be done by assessing symptoms, quality of life, anal continence and hemorrhoidal anatomy pre- and postoperatively.
Objectives:	Primary: Symptoms related to hemorrhoids one year postoperatively, according to a hemorrhoidal disease symptom score (HDSS) Secondary: 1) Patient satisfaction with the operation. 2) Health related Quality of Life 3) Anal continence as evaluated by two scores for symptoms of incontinence. All one year postoperatively
Population:	Male or female, ASA I-II, aged 18 to 85 at the time of randomization, referred to surgical assessment and presenting with grade II hemorrhoids refractory to banding or sclerosing and grade III og IV hemorrhoids at the surgical department, Holbæk Hospital.
Site:	Single center study. Holbæk Hospital, Surgical Department
Description of Intervention:	Hemorrhoidectomy with either Open Hemorrhoidectomy or LigaSure™ Hemorrhoidectomy
Study Duration:	48 months (from when the study opens to enrollment until completion of follow up.)
Subject Participation Duration:	One year
Estimated Time to Complete Enrollment:	36 months

Schematic of Study Design:

INTRODUCTION

Background

Hemorrhoids is one of the oldest known medical conditions. Description of hemorrhoids is found as early as 2250BC in the code of king Hammurabi in Babylon. Even though first recorded treatment is thought to be found in the "Edwin Smith Papyrus" from 1700BC¹ as of today the treatment of this benign state is still debated. A wide range of prevalence rates of hemorrhoids have been stated in part because of the varying definition, but the general consensus is that hemorrhoidal disease is a common anorectal disease affecting the quality of life of millions of people worldwide^{2 3}. Operation for hemorrhoid is one of the most common operations for benign disease in Denmark.

Hemorrhoids arise from the normal vascular structures in the anal canal also referred to as anal cushions or sinusoids as they do not contain muscular cells like arteries or veins. These cushions are typically arranged in three main columns or piles in the anal canal forming an important part of the intricate mechanism of the anal canal preventing incontinence⁴.

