Anal continence. OH and LH are both excisional operations. Anal continence has been a concern after these operations. Anal incontinence is defined as involuntary loss of air, liquid or solid stool that is a social or hygienic problem¹⁸. The anal cushions contribute to the closure of the anal canal and provide 15- 20% of maximal resting pressure of the anal canal¹⁹. A Cochrane review found that anal incontinence was reported in 1.6% of the patients after conventional hemorrhoidectomy²⁰. Another Cochrane review reported 3,6 % anal continence or hygiene problems at 1-2 years follow-up after conventional hemorrhoidectomy¹². When patients are actually asked for symptoms of incontinence a retrospective multicenter study found that 33% of the patients reported anal incontinence after hemorrhoidectomy and 10% meant this was caused by the operation²¹. Another study found some deterioration of anal incontinence after hemorrhoidectomy in patients with preoperative impaired continence²². Anal continence after LigaSure™ hemorrhoidectomy is scarcely investigated.

Previous studies comparing Open Hemorrhoidectomy and LigaSure™ Hemorrhoidectomy

Open Hemorrhoidectomy and LigaSure™ are both techniques where the hemorrhoids are excised, (ablative techniques). A few studies indicates that ablative techniques have better long term results in terms of reduction of symptoms^{11,23}.

There are so far 18 controlled studies comparing OH to LH²⁴⁻⁴¹, all designed for and using postoperative pain as major outcome variable. There are three metanalysis the largest including 11 studies^{42,43,44}. In conclusion there seems to be less post procedural pain, somewhat faster recovery, slightly less bleeding and shorter operating time after LH.

Patient' satisfaction was evaluated in a few studies with no difference between the two operations^{29,40,41}. One small study on 30 patients investigated anal continence with no difference between the two operations³⁰.

No study has investigated hemorrhoidal symptoms with a validated instrument one year or more after the operation

Rationale

Hemorrhoidal Disease is a benign disease and should be evaluated by its effect on hemorrhoidal symptoms together with its effect on quality of life.

Hemorrhoidal symptoms should be the main outcome variable when evaluating surgery for hemorrhoidal disease. This information is largely lacking.

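### Preoperative Wexner and RFIS scores are collected but have no role in the one-year continence comparison; ANCOVA on the preoperative score and gender would usually be more precise, with a gain that depends on an unstated correlation.

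*Combined protocol and SAP*

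**What the plan says.** The Objectives in the Précis list continence as a secondary outcome: "Anal continence as evaluated by two scores for symptoms of incontinence. All one year postoperatively". Under Evaluation of anal continence, both scores are to be completed by the patient on this schedule: "Evaluation will be done preoperatively at randomization, after 3 months, one-, three- and five years". Every patient should therefore have a preoperative value of each score.

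STATISTICAL CONSIDERATIONS holds a hypothesis and sample-size calculations and nothing else. It names no analysis model, covariate or change score for any outcome. For continence, Sample Size Considerations takes preliminary data from another study at the center: "a mean of 2,3 with an SD of 3,9 for the RFIS", while the Wexner average is 4 with the same spread. The section then sizes the comparison as follows: "To demonstrate a difference in mean score of 3 points with a SD of 3.9 in both groups", with 5% alpha and 20% beta, giving 27 per group. The calculator used for the primary outcome is described as "comparing the means for two independent samples with a two sided test has been used"; the continence calculation takes the same form.

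Under Randomization, "Randomization is stratified by gender". No blocking is mentioned, and gender is given no role in the analysis either.

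**The concern.** A preoperative score that predicts the one-year score explains part of the variation between patients. Leaving it out of the comparison discards that information and widens the confidence interval. The Background says of the newer operation: "Anal continence after LigaSure™ hemorrhoidectomy is scarcely investigated". It also cites a study in which continence worsened in patients whose continence was already impaired before surgery. Precision on this outcome therefore has value, and the preoperative score is a plausible predictor.

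There is also a question of specification. With no model named, the one-year score, the change from baseline and the baseline-adjusted score all remain available after the data are seen. They differ in precision and can give different answers. Naming one in advance removes that choice.

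**Working it through.** **Inputs from Sample Size Considerations:** difference 3 points, SD 3.9, two-sided 5%, 80% power, 31 evaluable per arm. The time point of the Wexner and RFIS preliminary data is not stated, so using 3.9 as the one-year SD is an assumption.

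**Input not in the documents:** the correlation r between the preoperative and one-year score. A range of 0 to 0.7 is shown.

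**1. The plan's figure.** n per arm = 2 × (1.960 + 0.842)² × 3.9² / 3² = 26.5, so 27. This reproduces the stated figure with no baseline term. (An exact t-test gives 27.5, so 28; the difference is immaterial.)

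**2. Unadjusted comparison at 31 per arm.** Standard error = 3.9 × √(2/31) = 0.991. With 60 degrees of freedom t = 2.000, so the half-width is 1.98. Noncentrality is 3 / 0.991 = 3.03, and power is 84.6%.

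**3. ANCOVA on preoperative score and gender.** Residual SD = 3.9 × √(1 − r²), assuming gender explains no further variance. Two covariates will be somewhat unbalanced between arms by chance, which multiplies the variance by about 1 + 2/57. Hence

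SE = 3.9 × √(1 − r²) × √(2/31) × √(1 + 2/57), with 58 degrees of freedom (t = 2.002).

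At r = 0.3: residual SD 3.720; SE = 3.720 × 0.2540 × 1.0174 = 0.961; half-width = 2.002 × 0.961 = 1.92; noncentrality = 3 / 0.961 = 3.12; power 86.6%.

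| r | Residual SD | Power | 95% CI half-width |
|---|---|---|---|
| Unadjusted | 3.90 | 84.6% | 1.98 |
| 0 | 3.90 | 83.3% | 2.02 |
| 0.3 | 3.72 | 86.6% | 1.92 |
| 0.5 | 3.38 | 92.2% | 1.75 |
| 0.7 | 2.79 | 98.4% | 1.44 |

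**4. Break-even.** The standard errors are equal when (1 − r²)(1 + 2/57) = 1, so r = √(2/59) = 0.18; allowing for the lost degrees of freedom it is about 0.19. With the preoperative score as the only covariate, r = √(1/59) = 0.13. The worst case, r = 0, costs 84.6 − 83.3 = 1.3 percentage points of power.

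**5. Cost of gender.** If allocation is not blocked within gender, simulation puts the widening of the half-width from adding gender at about 0.015 to 0.018 points. The formula agrees: at r = 0.3 the half-width is 1.907 with the preoperative score alone and 1.924 with both covariates.

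**6. The floor at 0.** A normal distribution with the stated moments puts 28% of RFIS scores (mean 2.3, SD 3.9) and 15% of Wexner scores (mean 4, SD 3.9) below 0, so the real scores must be skewed. In simulations with scores bounded at 0 to 20, matched to those means and SD, ANCOVA's type I error was 4.6% to 5.2% and its interval coverage 94.7% to 95.4%. Those simulations set the observed correlation in advance, so they do not show that the floor leaves r intact. With the same bounded distributions, an underlying correlation of 0.3 becomes an observed 0.27 (Wexner) or 0.22 (RFIS), and 0.5 becomes 0.47 or 0.40.

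**7. Change score, for comparison.** With equal SDs at both times, the SD of change is 3.9 × √(2(1 − r)). At 31 per arm, power is 71.2%, 84.6% or 97.0% at r = 0.3, 0.5 or 0.7.

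**The case against.** The strongest reply is that the gain may be trivial. At r = 0.3 it is 2 percentage points of power and 0.06 points of half-width on a 0 to 20 scale. Below about 0.19 the adjusted model is slightly worse. The floor lowers the observed correlation, and excluding patients incontinent for solid stool narrows the preoperative range further. All of this stands: the gain is conditional, and a reader should not take the adjustment to be free.

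A second reply is that this outcome is secondary, already exceeds 80% power, and is only one part of a wider gap, since the primary symptom score is also measured preoperatively without a stated role. That also stands. It limits the priority of the point and is a reason to extend the remedy, but it does not remove the case for it.

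A reader might infer three stronger things that the documents do not support. First, that the comparison as described is biased: it is not, because the arms are randomized. Second, that the trial will analyze change scores and fall to about 71% power: no change-score analysis is proposed anywhere, and that figure describes only one option left open, at one assumed correlation. Third, that simulation shows the gain survives the floor: it supports the validity of ANCOVA here, not the size of the correlation.

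**Conclusion.** The point holds, at low priority. It is certain that the preoperative continence scores are collected and that the plan gives them no analytic role. The size of the benefit is uncertain. Against 84.6% power and a half-width of 1.98, ANCOVA with both covariates ranges from a loss of 1.3 percentage points at r = 0 to a gain of 13.8 at r = 0.7 (98.4 − 84.6), with the low end plausible because of the floor. These figures assume 31 evaluable per arm, an SD of 3.9 applying at one year, normal-theory formulas and no extra variance explained by gender. Whatever the correlation, naming the model fixes the choice before the data are seen.

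**What to change.** State in STATISTICAL CONSIDERATIONS that:

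- One-year Wexner and one-year RFIS are each compared between arms by ANCOVA, with the preoperative value of the same score and gender (the stratification factor) as covariates.
- The adjusted difference is reported with its 95% confidence interval.
- A bootstrap confidence interval is the robustness check, because of the floor at 0.
- A missing preoperative score is replaced by the overall baseline mean, so that the patient stays in the analysis.

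This is a change of wording only. It needs no new data, visits or patients, and 31 per arm can stay. The statistical cost is at most about 1.3 percentage points of power if the preoperative score proves uninformative. The same sentence could be extended to the primary symptom score.
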